4.1. Inclusion Criteria

1. Patients undergoing CC and/or PCI via the radial artery as part of their standard of care treatment
2. Patients able and willing to give written informed consent
3. Patient ≥ 18 years of age

4.2. Exclusion Criteria

1. Patients presenting with acute ST segment elevation myocardial infarction (STEMI)
2. Oral anticoagulation therapy as described below:
 - a. If on a DOAC (direct acting oral anticoagulants – ie dabigatran, rivaroxaban, apixaban, edoxaban), patients will be excluded if DOAC taken within 48 hours and eGFR > 30 ml/min or DOAC taken within 72 hours and eGFR ≤ 30 ml/min.
 - b. If patient is on warfarin, excluded if INR > 1.5
3. Liver Failure
4. Life threatening illness that patient would not be expected to live more than 6 months post procedure
5. Major unanticipated event in the cardiac cath lab (i.e. cardiac arrest) of an already consented patient, but before randomization, where the operator believes participation in this trial is now inappropriate.

6. Thrombocytopenia, with a platelet count of < 75,000.

4.3. Subject Recruitment and Screening

All eligible subjects undergoing transradial coronary procedures from our hospital will be recruited directly by the investigators and research staff. The subjects will be asked in the pre-procedural unit if they wish to participate in this study comparing the two FDA approved hemostatic devices at the completion of their radial artery access procedure. The investigator or his qualified designee will then obtain written informed consent according to ICH GCP (International Conference on Harmonization Good Clinical Practice). The completed consent forms will be retained by the Investigator and a copy of the consent form will be provided to the study participant.

4.4. Method for Assigning Subjects to Treatment Groups

Subjects undergoing CC and/or PCI via the radial artery as part of their standard of care treatment, and who have signed informed consent, will be randomized in the cardiac cath lab upon completion of their procedures. The REDCap randomization tools will be used to facilitate randomization. A statistician will create a random allocation table (randomization list) that will be uploaded into the REDCap project. The statistician will generate the random allocation table according to study design specifications as determined by the statistician and principal investigator. Participants will be randomized when the research coordinator enters a participant's REDCap record and clicks the "Randomize" button before sheath removal by the physician. Clicking this button triggers REDCap to check the allocation table and display the group to which the participant should be randomly assigned. This assignment is permanent and not editable within the participant's record and, like all other activity within REDCap, is tracked and not modifiable in the audit log. All subjects randomized into the old arm 3 (QuikClot®/Tegaderm™) by REDCap will be considered screen failures, and all screen failed subjects per this amended protocol will be assigned into the new arm 3 (QuikClot®/TR Band®), and a data collection instrument for the new arm 3 will be developed and added to the REDCap for this trial.

4.5. Compliance Monitoring

The protocol will be monitored for compliance by the Principal Investigator with oversight by the Office of Human Research (OHR)'s Monitoring and Compliance Officer. The task of the study monitor is to guarantee the best conduct of the study through frequent contacts by phone and in person with the responsible Investigator and research nurse/specialist, in accordance with the Monitor's Operating Procedures, with the purpose of facilitating the work and fulfilling the objectives of the study.

The *QuikClot® Radial®* pad compression device and Coban™ bandages will be stored in a locked area and access will be limited to the research team. The *QuikClot® Radial®* pad compression device and Coban™ bandages will be only used as described in this trial. Subjects will receive the *QuikClot® Radial®* pad compression device and Coban™ bandages without charge.

5. Study Procedures

Participation in the study will involve two clinical visits as follows:

5.1. Visit 1 –At time of Standard of Care Cardiac Catheterization and/or PCI

All subjects will be closely monitored for bleeding from the radial artery access site. Monitoring will be continued until complete hemostasis from the radial artery has been achieved. Use of reapplication of the *QuikClot® Radial®* pad or a TR band® will be at the discretion of the investigator if hemostasis is not achieved at the end of compression period. One hour after complete hemostasis, the numeric analog pain scale will be administered and recorded by

the research coordinator, and then radial artery patency will be assessed by the research coordinator using the reverse Barbeau's test.²⁰

The research coordinator will then:

- Schedule a phone call (or bedside visit, if applicable, for those subjects still in the hospital) for Visit 2.
- Instruct the subject to call the research coordinator the day after enrollment to notify the research team of any occurrence of adverse events related to the application of either device. The subject may leave a message on the research coordinator's voicemail, if the research coordinator is not able to answer the telephone, with their condition and any adverse events. The voicemail will be checked daily. For any perceived serious adverse event by the subject, they should call the interventional cardiologist who performed the procedure or seek emergency care.

5.2. Visit 2-One day after enrollment

For subjects who are still in the hospital, the research coordinator will visit the subjects in their hospital room the day after the procedure, to assess the subject's condition and adverse events related to application of either hemostatic device. For patients who are already at home the day after their procedure, the research coordinator will contact the subjects by telephone one day after TRA to assess the subject's condition and adverse events related to application of either hemostatic device. If it is on weekend, the research coordinator will contact the subjects by telephone the next business day. For those subjects who cannot be reached by telephone on the first attempt, the research coordinator will make three attempts, once daily, to reach the subjects.

6. Safety and Adverse Events

6.1. Definitions

Adverse Event: An adverse event (AE) is any symptom, sign, illness or experience that develops or worsens in severity during the course of the study. Intercurrent illnesses or injuries should be regarded as adverse events.

Abnormal results of diagnostic procedures are considered to be adverse events if the abnormality:

- results in study withdrawal
- is associated with a serious adverse event
- is associated with clinical signs or symptoms
- leads to additional treatment or to further diagnostic tests
- is considered by the investigator to be of clinical significance

Serious Adverse Event: Adverse events are classified as serious or non-serious. A serious adverse event is any AE that is:

- fatal
- life-threatening
- requires or prolongs hospital stay
- results in persistent or significant disability or incapacity
- a congenital anomaly or birth defect
- an important medical event

Important medical events are those that may not be immediately life threatening, but are clearly of major clinical significance. They may jeopardize the subject, and may require intervention to prevent one of the other serious outcomes noted above. For example, drug overdose or abuse, a seizure that did not result in in-patient

hospitalization, or intensive treatment of bronchospasm in an emergency department would typically be considered serious. All adverse events that do not meet any of the criteria for serious should be regarded as non-serious adverse events.

6.2. Adverse Event Reporting Period

The study period during which adverse events must be reported is normally defined as the period from the initiation of any study procedures to the end of the study treatment follow-up. Only SERIOUS ADVERSE EVENTS will be reported on for this study.

Any adverse event that results in hospitalization or prolonged hospitalization should be documented and reported as a serious adverse event unless specifically instructed otherwise in this protocol. Any condition responsible for surgery should be documented as an adverse event if the condition meets the criteria for an adverse event. Neither the condition, hospitalization, prolonged hospitalization, nor surgery are reported as an adverse event in the following circumstances:

- Hospitalization or prolonged hospitalization for diagnostic or elective surgical procedures for a preexisting condition. Surgery should **not** be reported as an outcome of an adverse event if the purpose of the surgery was elective or diagnostic and the outcome was uneventful.
- Hospitalization or prolonged hospitalization required to allow efficacy measurement for the study.
- Hospitalization or prolonged hospitalization for therapy of the target disease of the study, unless it is a worsening or increase in frequency of hospital admissions as judged by the clinical investigator.

6.3. Recording of Adverse Events

All serious adverse events occurring during the study period must be recorded. The clinical course of each event should be followed until resolution, stabilization, or until it has been determined that the study treatment or participation is not the cause. Serious adverse events that are still ongoing at the end of the study period must be followed up to determine the final outcome.

6.4. Reporting of Serious Adverse Events

Reports of all serious adverse events (including follow-up information) will be submitted to the IRB within 10 working days. Copies of each report and documentation of IRB notification and receipt will be kept in the Principal Investigator's binder. The funding sponsor of *QuikClot® Radial®* pad will be notified of serious adverse events related to the device (FDA Medwatch report).

7. Data Handling and Record Keeping

7.1. Confidentiality

Information about study subjects will be kept confidential and managed according to the requirements of the Health Insurance Portability and Accountability Act of 1996 (HIPAA). Those regulations require a signed subject authorization informing the subject of the following:

- What protected health information (PHI) will be collected from subjects in this study
- Who will have access to that information and why
- Who will use or disclose that information
- The rights of a research subject to revoke their authorization for use of their PHI.

In the event that a subject revokes authorization to collect or use PHI, the investigator, by regulation, retains the ability to use all information collected prior to the revocation of subject authorization.

7.2. Data Management

Data management will be managed by OHR of Memorial Healthcare System. Study data will be collected and managed using REDCap electronic data capture tools hosted at OHR of Memorial Healthcare System. REDCap (Research Electronic Data Capture) is a secure, web-based application designed to support data capture for research studies, providing 1) an intuitive interface for validated data entry; 2) audit trails for tracking data manipulation and export procedures; 3) automated export procedures for seamless data downloads to common statistical packages; and 4) procedures for importing data from external sources. .

7.3. Sample Size and Statistics

Based on the previous study¹⁷ on the use of TR Band® and our pilot study on the *QuikClot® Radial®* pad with either a Coban™ bandage or Tegaderm™ dressing for radial hemostasis, we anticipate an average initial successful hemostasis rate of 95% or higher in patients using the *QuikClot® Radial®* pad compression device, compared to an initial successful hemostasis rate of 84% in patients using the TR Band®, and no significant differences between the two *QuikClot® Radial®* pad arms. Using a type 1 error of 0.05 for each of the two comparisons of the *QuikClot® Radial®* pad with the TR Band® and power of 80% to detect an 11% difference in the rate of initial successful hemostasis between the TR Band® arm and either *QuikClot® Radial®* pad arm, a sample size of 100 will be needed for each of the three arms of the trial. Assuming that there may be a 50% screen failure rate (patients withdraw, ulnar access is used, radial access failure, events occur during the procedure that the investigator does not wish to enter the subject or the diagnostic only cases of the study are already filled), a total of up to 600 consecutive subjects undergoing transradial diagnostic cardiac catheterization and/or PCI, who sign informed consent to participate, will be recruited into the three arms of the trial.

An interim analysis was not originally planned for the study, but was conducted after enrolling 186 participants. The results obtained from the interim analysis showed that there was a failure to obtain initial hemostasis at 5 minutes in approximately 30% of the subjects in the QuikClot®/Tegaderm™ arm of the protocol, compared to a failure to obtain initial hemostasis of 11% in the TR Band® cohort (odds ratio = 3.2, 95% CI, 1.2 – 8.1, $p = 0.013$) and a failure to obtain initial hemostasis of 8% in the QuikClot®/Coban™ cohort (odds ratio = 4.7, 95% CI, 1.7 – 12.1, $p = 0.003$). Our DSMB committee reviewed the results and recommended to stop the Tegaderm™ only arm. We here institute a new arm 3 using a QuikClot® Radial® Pad under a TR Band® with 30 minutes of compression to replace the old arm 3 in this trial. The sample size of the new arm 3 is the same as the old arm 3, with 100 participants including 50 diagnostic-only cardiac catheterizations and 50 PCIs.

Statistical summaries and analyses of data will be performed at Memorial Healthcare System. Descriptive analysis will be performed for all data including means and standard derivation or medians for continuous variables and proportions for categorical variables. The t-test will be used to describe the differences of clinical outcomes between the two compression devices after TRA, and a two-sided p-value of 0.05 will be considered to be statistically significant.

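### Amended section 7.3 keeps 80% power at 100 per arm without reassessment: its own rates give about 72% two-sided, and power is lower still if TR Band success is near the interim 89%

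*Combined protocol and SAP*

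**What the plan says.** All of the relevant text is in section 7.3, apart from the enrolment counts in section 3.1 and the endpoint definition in section 3.2.1.

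- **Planning rates.** For the pad, "we anticipate an average initial successful hemostasis rate of 95% or higher in patients"; for control, "compared to an initial successful hemostasis rate of 84% in patients using the TR Band".
- **Power.** "Using a type 1 error of 0.05 for each of the two comparisons" with TR Band, and "power of 80% to detect an 11% difference in the rate of initial successful hemostasis between the TR Band® arm" and either pad arm, giving 100 per arm. This sentence does not say whether the test is one-sided or two-sided.
- **Significance level.** The closing paragraph does: "a two-sided p-value of 0.05 will be considered to be statistically significant".
- **Interim result.** The unplanned analysis at 186 participants found about 30% failure in the Tegaderm-only arm, "compared to a failure to obtain initial hemostasis of 11% in the TR Band® cohort" and "a failure to obtain initial hemostasis of 8% in the QuikClot®/Coban™ cohort". Success was therefore about 89% and 92% in the two continuing arms.
- **Amendment.** "The sample size of the new arm 3 is the same as the old arm 3". No revised rate, detectable difference or power is given.

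Section 3.1 counts the 72 TR Band and 72 Coban patients already enrolled toward the final 100 in each of those arms.

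**The concern.** A power statement written before any data is carried through an amendment whose authors had already seen the control rate and one pad rate. The reported 3-point gap (89% v 92%) is much smaller than the planned 11 points, and the control rate is 5 points above the planning value. The patients behind those rates also make up a large part of the final TR Band and Coban arms.

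Initial hemostasis is the first-listed primary endpoint and the only one with a power calculation. A reader who trusts 80% would take a non-significant result as fair evidence that the pad and the TR Band perform alike. If the true power is well below 80%, that inference is unsafe.

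**Working it through.** **Inputs.** Planning rates 84% and 95%, n = 100 per arm, interim rates 89% and 92%, two-sided 0.05: all from section 7.3. Interim arm sizes are not reported; 186/3 = 62 per arm is an assumption.

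**Formula.** For the two-proportion test with pooled null variance, let δ be the difference, p̄ the mean rate and SE = √{[p1(1−p1)+p2(1−p2)]/n}. Then power = Φ{[δ − 1.96√(2p̄(1−p̄)/n)] / SE}.

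**1. The plan's own figure (84% v 95%).** p̄ = 0.895 and SE = 0.0426. The null term is 1.96 × √(2 × 0.895 × 0.105/100) = 0.0850. Power = Φ[(0.11 − 0.0850)/0.0426] = Φ(0.59) = 72%. Exact enumeration of the same test gives 74.9%; Fisher's test gives 66.2%. For 80% power, 121 per arm are needed. With one-sided 0.05, n = 95 and power at 100 is 81.8%, so the stated 80% fits only a one-sided test.

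**2. Sensitivity to a TR Band rate of 89%** (100 per arm, two-sided):

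| Pad rate | Calculation | Power | n per arm for 80% |
|---|---|---|---|
| 92% | Φ[(0.03 − 0.0813)/0.0414] | 11% | 1,499 |
| 95% | Φ[(0.06 − 0.0752)/0.0381] | 35% | 320 |
| 98.5% | Φ[(0.095 − 0.0671)/0.0336] | about 80% | about 100 |

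The 95% CI half-width is 1.96 × SE: 1.96 × 0.0381 = 7.5 points at 89% v 95%, and 1.96 × 0.0414 = 8.1 points at 89% v 92%. If TR Band ends at 89/100, a pad arm needs 97/100 for significance (z = 2.22; at 96/100, z = 1.88).

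**3. Conditional power given the interim patients.** Take 55/62 successes for TR Band, 57/62 for Coban and 44/62 for Tegaderm. These counts give odds ratios (18 × 55)/(7 × 44) = 3.2 and (18 × 57)/(5 × 44) = 4.7, as stated. The intervals match less well: 1.23–8.39 and 1.61–13.54, against the reported 1.2–8.1 and 1.7–12.1. The counts are therefore approximate. The remaining 100 − 62 = 38 per arm (and all 100 in Arm 3) are enumerated exactly.

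- **Coban v TR Band.** With 84%/95% from here on, the expected totals are 55 + 38 × 0.84 = 86.9 and 57 + 38 × 0.95 = 93.1, a gap of about 6 points. Conditional power is 20%. It is 5% at 89%/95% and 2% at the interim rates.
- **Arm 3 v TR Band.** With the remaining TR Band patients at 84%, conditional power is 54% if Arm 3 is truly 95%, and 84% if it is truly 97%. With them at 89%, it is 35% for a 95% Arm 3. If the interim TR Band group held 56 to 66 patients, the 54% moves between about 48% and 58%.

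**4. What the interim data can exclude.** The exact 95% CI is 78% to 95% for 55/62 and 82% to 97% for 57/62. The difference is 3.2 points (−7 to +14). If TR Band success is truly 84%, seven or fewer failures in 62 occur about 20% of the time.

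**The case against.** Design power is conditional on assumed rates, and power recomputed at an observed effect does not disprove those assumptions. Step 4 bears this out: 84%, 95% and 11 points all lie inside the interim intervals. This objection stands against reading the 11% and 35% as the true power of the trial. It does not touch step 1, which uses no interim data. Nor does it fully answer step 3: the interim outcomes are already part of the final TR Band and Coban arms, so the planning rates can now apply only to patients not yet counted.

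Three further points have force.

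- **Arm 3 has no reported trial outcomes.** The Coban rate says nothing about it, and the plan allows a pad rate above 95%. At 97%, with the rest of the TR Band arm at 84%, conditional power is about 84%. Arm 3 is affected only through the shared control arm.
- **The interim measure may differ from the primary endpoint.** Section 7.3 describes the Tegaderm failure as being at 5 minutes, whereas the TR Band stays inflated for 60 minutes before weaning and endpoint 3.2.1 is judged after the full protocol. The documents do not say that the two measures are the same.
- **Sidedness is not given in the sample-size sentence.** A one-sided 0.05 would support the stated 80%, but the only level the section states for analysis is two-sided.

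**Conclusion.** The point holds as a failure to reassess, together with a stated power that the plan's own inputs do not support. At 84% v 95%, two-sided 0.05 and 100 per arm, power is about 72% (75% exact). This rests only on figures in section 7.3.

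For the amended trial, power at an 89% control rate is about 35% against a 95% pad rate and 11% against 92%; reaching 80% needs a pad rate of about 98.5%. Conditional power at the planned rates is about 20% for Coban, and about 54% for Arm 3 at 95%. The conditional figures assume about 62 per arm at the interim and that the interim measure is endpoint 3.2.1.

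A reader might infer more: that the interim data prove the planning rates wrong, that an 11-point gain is now possible only with 100% success (89 + 11), or that a null result is to be expected in both comparisons. The documents do not support this. The first two treat an estimate from about 62 patients as the true control rate, and the third has no Arm 3 data behind it.

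**What to change.** In section 7.3:

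1. Label the 84%/95%/80% statement as the original planning basis, and correct its power at 100 per arm to about 72% two-sided.
2. Add a sensitivity statement for the amended trial: about 35% power at 89% v 95%, about 11% at 89% v 92%, and a 95% CI half-width of about 8 points. Mark it as conditional on an imprecise interim control rate.
3. State whether the interim failure rates are endpoint 3.2.1 in each arm.
4. State that each pad-versus-TR Band conclusion on initial hemostasis will rest on the difference in proportions with its 95% CI, and that non-significance will not be reported as equal hemostasis.

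I would not add a non-inferiority margin now, because comparative interim rates are already known. The cost is wording only, with no extra patients; the downside is that the stated power becomes less favourable.

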Our pilot study in 30 patients undergoing TRA demonstrated that application of the *QuikClot® Radial®* pad with 5 minutes of manual compression followed by a light compressive elastic bandage supplied by Z-Medica LLC for 25 minutes or 55 minutes achieved 100% hemostasis following TRA, with no increased complications noted (see Table below).¹⁵

Post-procedure outcomes with the use of QuikClot® Radial® pad

	TR Band® (n = 10)	QuikClot® 30 min. (n = 10)	QuikClot® 60 min. (n = 10)	P Value
Compression time (min)	149.4 ± 36.5	30.7 ± 2.2	60.9 ± 2.9	< 0.001
Initial hemostasis	5 (50%)	10 (100%)	10 (100%)	< 0.001
Pain scale	0	0	0	NS
Recovery unit time (min)	263.3 ± 56.3	238.9 ± 114.8	237.6 ± 71.6	NS
Access-site complications				
Radial artery occlusion	0 (%)	0 (0%)	0 (0%)	NS
Hematoma	0 (0%)	1 (10%)	0 (0%)	NS
Ecchymosis	0 (%)	0 (0%)	1 (10%)	NS
Edema	0 (%)	0 (0%)	0 (0%)	NS
Rebleeding	0 (%)	0 (0%)	0 (0%)	NS
Other	0 (0%)	0 (0%)	0 (0%)	NS

Results are mean ± standard deviation or n (%); NS, Not significant

Our recent other preliminary study (data not yet published) further demonstrated that application of the *QuikClot® Radial®* pad with 5 minutes of initial manual compression following by 25 minutes of light compression with either a Coban™ bandage or Tegaderm™ dressing was successful in all 20 patients who underwent diagnostic cardiac catheterization and/or PCI, with 100% hemostasis without rebleeding, RAO, and other complications. This preliminary clinical evaluation suggests that the *QuikClot® Radial®* pad combined with either a Coban™ bandage or Tegaderm™ dressing is an easy to use and an effective hemostatic dressing that allowed for a short duration of compression and a painless hemostasis procedure. Thus, there is a need to assess the true efficacy and safety of the *QuikClot® Radial®* pad combined with either a Coban™ bandage or Tegaderm™ dressing in the management of radial hemostasis following TRA in a larger number of patients.

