3.2. Primary Study Endpoints

3.2.1. Initial successful hemostasis: Initial successful hemostasis is defined as no evidence of external bleeding from the TRA puncture site or expanding hematoma of the forearm after completion of the above described TR Band® and *QuikClot® Radial®* pad protocols, without the need for reinflation of air in the TR Band® or reapplication of manual pressure over the *QuikClot® Radial®* pad secured with a Coban™ bandage, or use of manual compression over the arteriotomy site. If an EASY grade class 1 forearm hematoma (see below section 3.3.3) develops while either hemostatic device is in place and is successfully treated without altering the weaning protocol of either device (i.e. the need for reinflation of air upon weaning the TR Band® or manual recompression of the *QuikClot® Radial®* pad after the initial 5 minute hold), this will be considered successful hemostasis.

3.2.2. Total time to hemostasis: Total time to hemostasis will be calculated as the time needed from sheath removal to achieving complete hemostasis, as described below:

For the *QuikClot® Radial®* pad + Coban™ bandage arm, total time to hemostasis includes the initial 5

minutes of manual compression and 25 minutes of light compression with the Coban™ bandage, and plus any additional protocol directed recompression time needed to obtain complete hemostasis.

For the *QuikClot® Radial®* pad + TR band® arm, total time to hemostasis includes the initial 30 minutes of compression plus 1 minute of weaning, and any additional protocol directed recompression and/or weaning times needed to obtain complete hemostasis.

[figure not shown]
For the standard of care TR Band® arm, total time to hemostasis includes the initial 60 minutes of compression plus 60 minutes of weaning, plus any additional protocol directed recompression and/or weaning time needed to obtain complete hemostasis.

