3.3. Secondary Study Endpoint

3.3.1. Radial artery occlusion (RAO): RAO will be assessed one to two hours after completed hemostasis, using the reverse Barbeau's test.²⁰ Completed hemostasis in the TR Band® cohort will be after the device is removed and the puncture site is covered with a Band-Aid or a dry gauze pad under a Tegaderm™ dressing without further bleeding/oozing from the access site or development of a forearm hematoma. Completed hemostasis in the *QuikClot® Radial®* pad/Coban™ cohort is defined as no further bleeding/oozing or development of a forearm hematoma after the Coban™ bandage is removed and the *QuikClot® Radial®* pad is secured with a Tegaderm™ dressing. Completed hemostasis in the QuikClot®/TR Band® cohort will be after the TR Band® is removed without further bleeding/oozing at the access site or development of a forearm hematoma. RAO is evaluated one to two hours after completed hemostasis based on previous findings which demonstrated the highest incidence of RAO immediately after band removal.¹¹

3.3.2. Patient comfort/pain: Patients will be asked to rate their comfort level associated with the hemostatic device they have been assigned. A verbal numeric rating scale (VNRS) will be utilized to evaluate patient comfort with each device. This scale will use a 0 to 10 numeric rating to assess overall discomfort or pain related to the access site compression with each device, where 0 indicates no discomfort or pain at all and 10 indicates the worst pain the patient can imagine. The research coordinator will review the VNRS with each patient just prior to assessment of radial artery patency with the reverse Barbeau's test.²⁰ The research coordinator will record the patient's response.

3.3.3. Access site complications: Complications related to the device will be followed up to resolution or discharge, whichever comes first. Research staff will observe and record bleeding and hematomas that occur related to the access site. The severity of bleeding and forearm hematoma will be recorded using the criteria of the Early Discharge after Transradial Stenting of Coronary Arteries (EASY) classification.²¹ See Figure below for radial artery hematoma classification. Cases of device failure, procedural difficulties, and evidence of vascular complications associated with the closure procedure will be recorded, and appropriate therapy will be given.

Radial Artery Hematoma Classification

Grade I	Grade II	Grade III	Grade IV	Grade V

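### The t-test is the only inferential test named and no method is given for binary outcomes; for rare events at unequal rates the interval it implies under-covers

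*Combined protocol and SAP*

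**What the plan says.** The analysis plan is a short paragraph at the end of section 7.3 of the combined protocol and SAP. Its one inferential method is: "The t-test will be used to describe the differences of clinical outcomes between the two compression devices after TRA". The significance rule is that "a two-sided p-value of 0.05 will be considered to be statistically significant". Everything else is descriptive: "Descriptive analysis will be performed for all data including means and standard derivation or medians for continuous variables and proportions for categorical variables". No test, effect measure or confidence interval for proportions is named for the final analysis.

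The outcomes are mostly not continuous:

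- Section 3.2.1, a primary endpoint, is success or failure: "Initial successful hemostasis is defined as no evidence of external bleeding", with further conditions on reinflation and recompression.
- Section 3.3.1 is occluded or patent: "RAO will be assessed one to two hours after completed hemostasis", by the reverse Barbeau test.
- Section 3.3.3 records access-site complications, with hematoma on the five-grade EASY scale.
- Only total time to hemostasis (3.2.2) and the 0-10 pain score (3.3.2) are numeric.

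The sample size in section 7.3 rests on proportions, with "power of 80% to detect an 11% difference in the rate of initial successful hemostasis". It also plans more than one contrast: "Using a type 1 error of 0.05 for each of the two comparisons" of a QuikClot arm with TR Band. The t-test sentence speaks of two devices, while section 3.1 has three arms.

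**The concern.** A plan that sizes the trial on a difference in proportions should say how proportions will be compared. Taken literally, this one applies a t-test to 0/1 data.

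The safety comparisons are where this could matter. The study objective covers safety as well as efficacy (section 2), and with 100 per arm there may be few RAO events. The useful result is then how large a difference the data can exclude, which depends on the interval. The t interval estimates its variance from the observed counts, so when few events are seen it is short, and when none are seen it has no width.

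Low counts are possible here. The second pilot reports "with 100% hemostasis without rebleeding, RAO, and other complications" in 20 patients, and the first reports no RAO in 30 (section 1.4).

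**Working it through.** **Inputs.** 100 per arm; 84% v 95% initial hemostasis; two-sided 0.05 (all section 7.3). RAO up to 8% (section 1.1); no RAO in 30 + 20 = 50 pilot patients (section 1.4). The documents give no RAO rate by arm, so every rare-event rate below is an assumption. Zero of 50 has a one-sided 95% upper limit of 1 - 0.05^(1/50) = 5.8%, so the pilots do not exclude rates of several percent.

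**The plan's own figure.** The usual two-proportion formula with mean rate 0.895 gives [1.960 × √(2 × 0.895 × 0.105) + 0.842 × √(0.84 × 0.16 + 0.95 × 0.05)]² / 0.11² = 1.461 / 0.0121 ≈ 121 per arm. The stated 100 is not reproduced (72.1% power by this formula). That is a separate matter; 100 is used here only as the arm size.

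**Method.** With equal arms, the t interval for observed rates a and b is (a - b) ± 1.972 × √{[a(1 - a) + b(1 - b)] / 99}. The Newcombe interval combines the Wilson limits (l, u) of each arm: lower limit (a - b) - √[(a - l_a)² + (u_b - b)²], and the mirror image for the upper. Coverage is the sum, over all pairs of counts from two Binomial(100, p) arms, of the probability of each pair whose interval contains the true difference.

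| True rates | t interval | Newcombe |
|---|---|---|
| 84% v 95% (primary) | 94.8% | 95.5% |
| 8% v 4% | 95.0% | 96.0% |
| 8% v 2% | 94.4% | 96.7% |
| 5% v 1% | 92.9% | 97.2% |
| 4% v 1% | 90.2% | 97.5% |
| 2% v 1% | 86.0% | 99.1% |
| 8% v 8% | 94.9% | 95.9% |
| 5% v 5% | 95.6% | 96.4% |
| 2% v 2% | 96.0% | 98.4% |

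**Type I error of the t-test.** At equal rates of 1%, 2%, 3%, 5% and 8% it is 1.4%, 4.0%, 4.5%, 4.4% and 5.1%, the same as Pearson chi-square. At 84% v 95% both tests have exact power 74.9%.

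**Direction of the misses.** At 4% v 1%, 9.0% of t intervals stop short of the true 3-point difference and 0.8% lie wholly beyond it (nominal 2.5% each side).

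- If QuikClot has the 4%, the upper limit for excess harm is too low 9.0% of the time.
- If QuikClot has the 1%, the same misses understate its benefit, and the upper limit for harm is too low only 0.8% of the time.

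**No events in either compared arm.** The probability is (1 - p)^200: 0.99^200 = 13% at a true rate of 1% in both arms, 0.98^200 = 1.8% at 2%, and about 0 at 5%. The t statistic is then 0/0 and the interval 0 to 0. The Wilson upper limit for 0/100 is 3.84 / 103.84 = 3.7%, so the Newcombe interval is -3.7 to +3.7 points.

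**No events in one arm.**

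- 1 v 0: t = 1.00, p = 0.32, interval -1.0 to 3.0 points; Newcombe -2.8 to 5.4.
- 4 v 0: standard error √(0.04 × 0.96 / 99) = 0.0197, t = 2.03, p = 0.044, interval 0.1 to 7.9 points; Newcombe -0.4 to 9.8.

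**The case against.** The case against making much of this is strong, and most of it stands.

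- The plan promises a test and a p-value, not a t interval. The interim results in section 7.3 are odds ratios with confidence intervals, so the team did not use a t interval for a binary outcome there. The coverage figures describe what the named test implies, not something the plan commits to.
- Type I error is sound, and the primary endpoint is essentially unaffected.
- Under-coverage needs rates that are both rare and unequal. Near the only RAO figure in the protocol, up to 8%, it is negligible.
- Sections 1.1 and 1.5 expect less RAO with shorter compression. If that is right, the bound on QuikClot harm is conservative.

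Stronger readings are tempting but unsupported. A reader might infer that the test breaks down whenever one arm is empty; it does not, as 1 v 0 and 4 v 0 show. Nor do the pilots make 0 v 0 a probable result: they allow rates of several percent, and the first pilot had one hematoma and one ecchymosis in its QuikClot arms, so complications in general were not absent. Finally, at 4 v 0 Fisher's exact test gives p = 0.12 against 0.044. This does not show that the t-test is wrong: chi-square gives 0.043, and Fisher's true size is only 1.1% at a 3% rate.

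What the objection does not remove is the gap itself: no method suited to proportions is specified for a trial whose primary, RAO and complication endpoints need one.

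**Conclusion.** The point holds as a specification gap with a limited numerical consequence. For initial hemostasis, changing the method alters almost nothing. For rare outcomes the implied 95% interval has coverage of about 86% to 94% at the unequal assumed rates from 2% v 1% to 8% v 2%. It is close to nominal at 8% v 4%, and at or above about 95% when the rates are equal. The documents do not support saying that safety is overstated as a rule: excess harm is wrongly excluded too often only if QuikClot is truly the worse arm. The undefined test with a zero-width interval needs no events in both compared arms.

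These figures assume 100 per arm, independent binomial counts and no stratification. The rare-event rates are not taken from the documents beyond the 8% ceiling and the absence of RAO in the pilots. This should be corrected before analysis, but it does not threaten the primary result.

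**What to change.** In section 7.3, replace the t-test for binary outcomes with the following:

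- For each QuikClot arm v TR Band separately, report the risk difference with a score 95% interval (Newcombe or Miettinen-Nurminen), stratified by diagnostic-only v PCI. Section 3.1 already fills each arm 50/50 on that factor.
- Name one test in advance for all binary outcomes, for example Cochran-Mantel-Haenszel to match the stratification. Do not switch to Fisher's test for events called rare: without a stated threshold that choice would be made from the data.
- For the graded hematoma outcome, state what counts as an event.
- Correct the reference to two devices so that the three arms and the planned contrasts are explicit.

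A rank test for pain is optional; the score was 0 in all three arms of the first pilot.

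The cost is wording and a little analysis work, with no extra patients. Intervals for rare events become wider: the expected unstratified width goes from 9.3 to 11.4 points at 5% v 1%, and from 6.4 to 9.6 at 2% v 1%. For the primary endpoint at 84% v 95% it goes only from 16.8 to 17.3.
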